PROTOCOL TITLE:

Decision Making & Implementation of Aging-in-Place/LTC Plans among Older Adults

PRINCIPAL INVESTIGATOR:

[name], MPH, MBA

General Internal Medicine & Geriatrics, Northwestern University Feinberg
School of Medicine

CO-INVESTIGATOR:

[name], MPH

General Internal Medicine & Geriatrics, Northwestern University Feinberg
School of Medicine

VERSION DATE:

01/29/22

1.0 Purpose of the study:

The purpose of this study is to better understand how older adult aging-in-place (AIP) decision making and implementation is impacted by age-related changes (e.g. cognition, function, chronic condition) and social influences. The specific aims of this study are:

Aim 1: Determine how decision making and planning for aging-in-place is impacted by older adults' age-related changes (e.g. function, cognition, multi-chronic conditions) and social influences (e.g. adult offspring, spouses, friends).

Aim 2. Examine contemplation of decision making, rates of existing service utilization, pre-existing attitudes and their potential for influence on older adult age-related changes and social influences in decision making for aging-in-place choices.

Exploratory Aim 3. Assess whether decision making and planning for aging-in-place translates into timely adoption and goal concordance for older adults and their surrogate/caregiver decision makers.

2.0 Background / Literature Review / Rationale for the study:

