4.0 Sample Size:

We plan on recruiting and enrolling a total 700 participants for this study. This sample size was determined given power calculations that will allow us to detect significance of our study outcomes.

5.0 Research Locations:

Participants will complete in-person research activities (written consent, baseline survey, intervention completion, and post-intervention survey) in research space available at the NMHC and Access Community Health Network (ACCESS) locations. Study follow-up surveys will take place over the phone.

ACCESS is a Public Health Service 330-funded network of community health centers, also known as Federally Qualified Health Centers (FQHCs). The LitCog study is linked to six ACCESS community health centers, however study participants will be able to complete the in-person study interview at only one of two ACCESS locations. Staff who are employed by ACCESS Community Health Network will not be involved in any aspect of recruitment, consent, data collection, and/or data analysis for this study.

ACCESS will only provide space for the in-person interview (if needed) and all consent & data collection procedures will be done by NU personnel if a participant wants to do the first study visit at an ACCESS location. All required permissions and/or approvals will be obtained at each research location prior to project implementation and submitted to the IRB.

6.0 Multiple sites:

Northwestern Medicine Division of General Internal Medicine and Geriatrics (GIM-GER) at the Feinberg School of Medicine will take the lead in collecting and storing the study data captured across this study in Aims 1, 2, and 3. Protocols, consent documents, and all data collection instruments will be disseminated to all study staff to ensure that everyone has the most up to date versions.

7.0 Reliance Agreements/Single IRB:

N/A

8.0 Procedures Involved:

Currently enrolled LitCog study participants (STU00026255) who have completed either T4 or T5 of that study will be invited to participate in this new, longitudinal, observational study. Interested participants who meet the study criteria will schedule a time for the in-person interview which will occur in research space available at the NMHC or the ACCESS locations, whichever is preferred by the participant and available to the study.

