Statistical analyses will be carried out by the statistical analysts in SAS 9.4 PROC GLIMMIX. For **Aim 1** we will model the association between decision making and planning for aging-in-place (= outcome) and the predictors age-related changes (e.g. cognition, health literacy, multi-chronic conditions) and social influences (e.g. adult offspring, spouses) using generalized linear mixed-effects regression models (GLMM) over the time period of 0-36 months post-baseline. This model allows us to incorporate outcome variables that are continuous, dichotomous, and other types such as count, ordinal, and nominal variables. GLMM are well fit for modeling longitudinal data by allowing us to incorporate random effects, which account for repeated measurements on participants over multiple time points. Additionally, the model uses all available data; not requiring all participants to have complete data.

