Structural Equation Modeling (SEM) will be performed to model relationships between cognitive function, health literacy, self-management skills, and aging-in-place outcomes (decision making, implementation, goal concordance) along with various mediating and/or moderating variables. SEM is an analytical technique in which a hypothetical model specifies the anticipated relationships between a series of constructs based on theory. Several statistical techniques (eg, confirmatory factor analysis, path analysis, regression) may also be seen as special cases of SEM methods. SEM follows 5 steps: 1) model specification, 2) model identification, 3) estimation of the model, 4) testing model fit, 5) re-specification, if needed. It is particularly useful when observed variables contain measurement error, are interdependent, and when potentially important explanatory variables (e.g. explicit resource knowledge, experiences) are not included in a model. Each of these cases applies to our models. In addition to allowing for comparisons of relative values of direct pathways within a model, SEM provides an explication of total effects of each factor on outcome variables by including information about indirect/direct effects of each exogenous and mediating variable on the outcomes. We predict that latent constructs of health literacy, self-management skills, and usage of PlanYourLifespan.org will mediate relationships between cognitive function and aging-in-place outcomes. In addition, treatment burden, social support, patient activation, and personality will moderate these associations. We are proposing to model change in these latent constructs over the 42 months in a multi-wave model. At each time point, we will model the mean level as well as the change (slope) in level of the latent variables. Growth curve parameters will be modeled similarly across all sets of constructs.

9.0 Incomplete Disclosure or Deception:

N/A

10.0 Recruitment Methods:

Participants who are currently enrolled in the LitCog observational study [R01AG03611, PI: [name]], (STU00026255) and have completed either time point 4 (T4) or time point 5 (T5) of that study will be offered the opportunity to participate in this study. There are currently over 700 older adults who are currently enrolled in the LitCog study.

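### The SEM plan counts omitted explanatory variables as a reason to use SEM, but an omitted common cause still biases the mediator-outcome paths, and no adjustment or sensitivity analysis is named

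*Combined protocol and SAP*

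**What the plan says.** The SEM paragraph of Section 8.0 (Statistical Analyses) gives three situations that favour SEM: variables measured with error, variables that depend on each other, and the situation "when potentially important explanatory variables (e.g. explicit resource knowledge, experiences) are not included in a model. Each of these cases applies to our models".

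The same paragraph predicts that "latent constructs of health literacy, self-management skills, and usage of PlanYourLifespan.org will mediate relationships between cognitive function and aging-in-place outcomes". It says SEM will set out total effects "by including information about indirect/direct effects of each exogenous and mediating variable on the outcomes". The outcomes are "aging-in-place outcomes (decision making, implementation, goal concordance". The model is longitudinal: "At each time point, we will model the mean level as well as the change (slope) in level of the latent variables".

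The only other variables named for the SEM are moderators: treatment burden, social support, patient activation and personality. The only checks named are a test of model fit and re-specification if needed. Neither the paragraph nor the rest of the document names confounders, adjustment covariates or a sensitivity analysis for the mediation paths. The measures table in Section 8.0 lists Previous Health Experiences, Healthcare Utilization, and living will and power of attorney, and the text above it adds sociodemographics. None of these is assigned to the SEM as a covariate.

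**The concern.** The study is observational and none of the three mediators is randomised. When a mediation model leaves out an important variable, that is a weakness of the model, whatever the fitting method. SEM absorbs omitted variables into the residual terms. This is harmless for a mediator-outcome path only if the mediator and outcome residuals are uncorrelated, and the plan never states that assumption. The plan's own examples, resource knowledge and experiences, could plausibly affect both use of the website and later planning.

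What is at stake is the interpretation of the indirect effects. The SEM paragraph is the only analysis text that names implementation and goal concordance as outcomes, and Exploratory Aim 3 asks whether planning "translates into timely adoption and goal concordance for older adults". A confounded indirect effect could be read as evidence that website usage or self-management carries the effect of cognition, or a real one could be hidden.

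**Working it through.** **The plan's own figure.** Section 4.0 gives 700 participants and refers to power calculations, but states no alpha, power, effect size or dropout. It cannot be reproduced. It is used below only as the sample size.

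**Model (all path values assumed).** C is cognition, M a mediator, Y an outcome and U the omitted variable. C and U are independent, and all four have unit variance.

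- M = aC + u_m·U + error
- Y = bM + c′C + u_y·U + error
- a = 0.3, c′ = 0.2, u_m = u_y = u

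**Bias when U is left out.** Since var(M given C) = 1 − a² = 0.91:

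- estimated b = b + u_m·u_y/0.91
- estimated direct effect = c′ − 0.3·u_m·u_y/0.91
- total effect c′ + ab is unchanged, because U is independent of C

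If u_m or u_y is zero, the bias is zero.

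**True b = 0, N = 700.** SE(b) = √[(1 − R²)/(700 × 0.91)], which is about 0.039. At u = 0.3, R² = 0.0989 × 0.15 + 0.1703 × 0.2 = 0.049, SE = √(0.951/637) = 0.0386 and z = 0.0989/0.0386 = 2.56. The rejection rate at two-sided 5% is then about Φ(2.56 − 1.96) = 0.73. Path a is practically always significant at this N, so this is also the false-positive rate of the joint-significance test. Simulation agrees:

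| u | Estimated b (true 0) | False indirect effect, 0.3 × b | Direct effect (true 0.2) | False positives, continuous Y |
|---|---|---|---|---|
| 0.1 | 0.011 | 0.003 | 0.197 | 6% |
| 0.2 | 0.044 | 0.013 | 0.187 | 20% |
| 0.3 | 0.099 | 0.030 | 0.170 | 72% |

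**Binary outcome.** The measures table describes the 36-month primary decision-making outcome as coming from binary and open-ended questions. Cutting Y at assumed prevalences of 50%, 30% and 10%, with a linear-probability test, gives about 14%, 14% and 11% at u = 0.2, and 53%, 48% and 32% at u = 0.3.

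**Variations (continuous Y, N = 700).**

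- U acting on one side only: about 5%.
- U itself adjusted for: about 5%.
- Path from U to the mediator halved, as bounded website time might do: 6%, 9% and 25%.
- True indirect effect 0.060 (b = 0.2): estimated as 0.063, 0.073 and 0.090. With opposite-sign paths of 0.2 and 0.3 it is estimated as 0.047 and 0.030, so the bias can go either way.

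**Does the fit test catch it?** A latent SEM with three indicators per construct, loadings of 0.8, c′ = 0.1 and u = 0.3 was fitted to the population covariance without U. It returned b = 0.099 where the truth is 0, a direct effect of 0.070 where the truth is 0.10, and a model chi-square of 0.0 on 24 df. Correcting for measurement error did not remove the bias, and the fit test could not see it.

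**Levels and slopes (an assumption only).** The documents do not show health literacy and self-management measured at every survey. Assume nine complete measurements over months 0 to 42, level reliability 0.8 and two-stage regression at N = 700:

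- U on levels only: the level path rejects in 6%, 15% and 52%; the slope path stays at 5%.
- U on slopes only: the slope path rejects in 6%, 15% and 52% at slope reliability 0.8, and in 5%, 9% and 21% at 0.5.

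**How much would adjustment recover?** If a single yes/no item cuts a continuous experience, the share of bias left is 1 − φ(z)²/[p(1 − p)]. That is 36% at an item prevalence of 50% and 66% at 10%. At u = 0.3 false positives fall from 72% to between 17% and 39%.

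**The case against.** The best case for the plan has several parts.

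- **The growth model gives some protection.** This stands. A stable past experience that shifts only levels leaves slope paths unharmed.
- **The moderators may condition on part of the confounding.** This stands in part. If they enter with main effects, which is usual but not stated, the model conditions on them. The plan does not present them as confounder control, and they do not cover the omitted variables it names itself. The illustrations above have no covariates.
- **The 72% is the wrong headline for a binary outcome.** This stands; 32% to 53% is closer to that outcome type, and every figure rests on assumed paths.
- **Website usage is constrained.** Section 8.0 allots 15 to 45 minutes, and under Section 12.0 those who do not complete the intervention leave the study. Self-selection therefore acts mainly on time within that range and on later use, which limits the bias but does not remove it.
- **Mediation appears in no numbered aim, and Aim 3 is exploratory.** True, and it limits the weight of the point.

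A reader might infer that the plan claims SEM removes confounding. It does not; it only counts omission among the situations where SEM is useful. A reader might also infer that Aim 1 is undermined. The mixed model there, in which "we will model the association between decision making and planning for aging-in-place (= outcome", is a separate analysis and this point does not reach it.

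**Conclusion.** The rationale is wrong as written, and following the plan can give a biased indirect effect that its own fit test need not detect. The bias requires a variable that affects both a mediator and an outcome, and it reaches slope paths only if that variable affects slopes. Cognition's total effect is unbiased in the linear model if the omitted variable is independent of cognition.

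The size cannot be learned from the documents. Under the assumed paths, a weak common cause (0.1) hardly matters and a moderate one (0.3) matters a good deal. It would be too strong to say that all planned paths are invalid or that any one of these error rates is to be expected. Whether the plan's reference to experiences means the Previous Health Experiences items is an inference, and the conclusion does not depend on it. This is a cheap improvement, confined to the SEM mediation analysis.

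**What to change.** 1. Delete the clause presenting omitted explanatory variables as a case suited to SEM. State instead that the mediation paths assume no unmeasured common cause of mediator and outcome.
2. For mediation through website usage, adjust the usage and outcome equations for collected variables that precede website use: the binary Previous Health Experiences items (with a stated coding rule), age and sociodemographics. Add baseline living will and power of attorney, and utilization from an earlier LitCog wave, once the instruments confirm the timing. An earlier wave should exist, because participants "who have completed either T4 or T5 of that study will be invited to participate". Fit this model separately from the health-literacy and self-management mediation. Prior planning or utilization may be consequences of those mediators and should not be adjusted away there.
3. As the main safeguard for all three mediators, report a sensitivity analysis that varies the mediator-outcome residual correlation, for levels and for slopes where both are modelled. Give the value at which each indirect effect disappears.

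**Cost.** Extra analysis work and no new data. Five single-parameter covariates in the usage equation and one outcome equation add 5 × 2 = 10 parameters, or 20 if they predict both levels and slopes. With three outcomes in one level-and-slope model the count is 5 × 4 × 2 = 40. Adjustment will be only partial, because the experience items are non-validated and partly open-ended. Resource knowledge is left to the sensitivity analysis.

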At the in-person study visit, participants will provide written informed consent using procedures approved by the Institutional Review Board of Northwestern University. Research staff will then administer a baseline study survey. Next, research staff will introduce subjects to the intervention, the PlanYourLifespan.org website, and provide instructions on its use. Research staff will be present to assist with questions as needed on navigation but will not assist with decision making or any content-related questions. A minimum of 15 minutes and a maximum of 45 minutes will be allotted for navigating the website. After completing the time allotted on PlanYourLifespan.org, subjects will administer an immediate post-test survey.

There will be a total of 8 follow-up surveys. Research staff will contact participants to complete a follow-up survey one month after the in-person interview, and then every six months thereafter. Follow-up surveys will be administered over the phone by research staff.

A maximum of five phone calls and two voice mail messages will be left for study participants. If after five phone call attempts have been made and the participant is not able to be reached, they will be considered 'unable to reach' for that time-point. Study coordinators will continue to reach out to study participants for the subsequent follow-up surveys. All follow-up phone surveys will have a target completion of at most 4 weeks from the scheduled follow-up interval.

The anticipated duration of this study is 42 months, or 3.5 years, from the time of consent to the completion of the final, follow-up study survey. Study participants will not be engaged in the study during that entire period.

Time (months)	0	1	6	12	18	24	30	36	42
Survey Modality	In-person pre and post-test	Phone							

The in-person meeting which will include the written consent (10 mins), baseline survey (30 mins), navigation of PlanYourLifespan.org (min: 15 minutes, max: 45 minutes), and

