completion of the post-intervention survey (15 mins) is expected to take between 70 minutes and 100 minutes of the subject's in-person time. Each follow-up survey is expected to take 15 minutes to complete, and with 8 planned follow-up surveys, they may collectively take participants up to 120 minutes, or approximately 2 hours to complete. These 15-minute follow-up surveys will be spaced out over 6-month periods. Therefore the total time of participation if all study components are completed is estimated to be between 190 – 220 minutes (approximately 3-3.5 hours).

Study data will come from multiple sources and includes (1) self-reported data by the study participant, (2) data that has been previously collected from the study participants from their participation in the LitCog study (e.g. cognition data), and (3) retrieving data from the participant's electronic health record. All of the electronic health records data we plan to analyze from this study will already be collected for the LitCog study. No additional electronic health records data will be accessed for this study.

We will collect a wide range of measurements such as process outcomes, cognition variables, functional and health variables, and social/environmental variables. Additionally we will collect sociodemographic variables, such as race and ethnicity, an assessment of PlanYourLifespan.org, and timing and goal concordance. The table below illustrates the measures/data that will be collected in this study. Data collection materials for each time point are submitted with this application.

	MEASURES	DETAILS	LITCOG Collected
PROCESS OUTCOMES			
Previous Health Experiences: Self & Others	Participant's past health experiences with self, others.	Non-validated binary & open-ended questions.	
Contemplation: Hospitalizations	Participant's thoughts about issues related to hospitalizations	Non-validated, Likert scale. Modified ACP questions.	
Decision-Making: Hospitalizations	Decision making specifically related to hospitalizations	Non-validated, open-ended	
Healthcare Utilization	Hospitalization + Rehabilitation; Emergency Department Visit; Urgent care visits (RUI); Medical Supplies (RUI); Physical therapy/occupational therapy (RUI); Long Term Care Facility Use	individual items, Sano, 2006	X
Contemplation: AD & Memory Loss	Participant's thoughts about issues related to AD & memory loss.	Non-validated, Likert scale. Modified ACP questions.	

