In order to ensure that participants fully understand the study and procedures, an individual’s consent capacity will be assessed by discussing the proposed study and then asking specific questions requiring descriptive answers. For example: *Can you tell me the purpose of this study? Do you have to be in this study? Can you tell me what will happen if you agree to take part in this study? How might this study help or not help you? What will happen if you decide not to be in the study?* If a participant correctly responds to these questions, they are deemed able to provide informed consent.

All participants will be given a copy of the signed consent form to keep for their records; the original will be kept on file at Northwestern University by the study team and also documented on the Study Tracker (formerly eNOTIS). Our study consent will require HIPAA Authorization given the electronic health record data collection and use of the LitCog data. The HIPAA Authorization language will be included in the consent form.

12.0 Financial Compensation:

Participants will be compensated for their time and participation. Participants will receive \$100 in cash for completing all of the in-person interview activities. If a participant is only able to complete the in-person interview partially, they will be compensated in the

following manner: \$25 for the pre-test survey, \$50 for the PlanYourLifespan.org intervention completion, and \$25 for the post-intervention survey. Participants who do not complete the intervention and/or the post-intervention survey will not be eligible for completion of the phone follow-up surveys and that will mark the end of their participation in the study.

Participants will also be compensated for the completion of the follow-up phone surveys. Participants will receive a \$50 Target gift card for the completion of each follow-up phone survey. There will be a maximum of 8 follow-up phone surveys (month 1 – month 42), for a maximum total of \$400 in Target gift cards during the follow-up period. Target gift cards will be used to compensate participants for the completion of phone follow-up surveys since the compensation will be mailed to study participants and we are unable to safely mail cash. The distribution of the financial compensation is specified below:

	Day of Intervention			Follow-Up Survey Months								TOT
	Baseline Survey	Intervention Completion	Post-PYL Survey	1	6	12	18	24	30	36	42	

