Subject	\$25	\$50	\$25	\$50	\$50	\$50	\$50	\$50	\$50	\$50	\$50	\$500
Cash	x	x	x									\$100
Gift Card				x	x	x	x	x	x	x	x	\$400

Participants will only be compensated for the research activities they complete. Therefore, if a participant completes all three parts of the in-person interview, and all 8 follow-up surveys, they will receive a maximum compensation of \$100 in cash and \$400 in Target gift cards. If they miss any of the phone follow-up surveys, they will not receive a gift card for those surveys. If a participant withdraws from the study, they will only receive compensation for the surveys they complete.

Participants who communicate to study coordinators that they would like to participate in the study but need transportation to/from the in-person interview will be reimbursed for travel. Participants that take public transportation will be reimbursed \$5 in cash. If a participant cannot access public transportation, they may be offered assistance by the study coordinators, depending on how far the participant lives. The coordinators will help to arrange for transport using ground transportation such as an Uber Health Ride or a pre-paid cab via Curb. Participants that need wheelchair accessible vehicles and use PACE to get to/from the study will be reimbursed the cost of their PACE ride. The cost of this transportation will be incurred by the research study, not the study participant.

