13.0 Audio/Video Recording/Photography

N/A

14.0 Potential Benefits to Participants:

Participants in this study may experience a direct benefit from being exposed to the intervention, PlanYourLifespan.org. As a result of being exposed to this resource,

participants may increase their knowledge of home-based resources and aging-in-place/long term care planning options.

15.0 Risks to Participants:

There are minimal risks to participation in this study. Some participants may face emotional discomfort in answering questions and thinking about their aging-in-place and long term care plans. During the consent process, participants will be informed that they may choose not to answer any question(s) they do not feel comfortable answering. They will also be informed that their involvement in the study is voluntary and they may withdraw from the study at any time.

We anticipate there may be special circumstances where a participant would be withdrawn from the research without their consent by the person in charge of the research study. Possible reasons for removal include having a stroke or other medical event that may make it too difficult for the participant to respond to the interviewers' questions and participate in study tasks. We will inform the participant about any new information that may affect their health, welfare, or choice to stay in the research study.

16.0 Provisions to Protect the Privacy and Confidentiality of Participants and the Research Data:

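### Missing only the 15-minute post-test ends all eight phone follow-ups, including the month-36 primary outcome; keeping website completers in follow-up would be a cheap improvement

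*Combined protocol and SAP*

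**What the plan says.** Section 12.0 (Financial Compensation) pays for the first visit in three parts: $25 for the baseline survey, $50 for the website session and $25 for the post-test. It then adds an exit rule: "Participants who do not complete the intervention and/or the post-intervention survey will not be eligible for completion of the phone follow-up surveys". For these people, participation in the study is over.

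Section 8.0 (Procedures Involved) puts the post-test last in the visit: "After completing the time allotted on PlanYourLifespan.org, subjects will administer an immediate post-test survey". It schedules eight phone surveys, at months 1, 6, 12, 18, 24, 30, 36 and 42, each expected to take 15 minutes. Its measures table marks decision making on AD and memory loss as the primary outcome at 36 months.

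Missed phone surveys are treated differently. Under section 8.0, when someone cannot be reached at one wave, "Study coordinators will continue to reach out to study participants for the subsequent follow-up surveys". Under section 12.0, "If they miss any of the phone follow-up surveys, they will not receive a gift card for those surveys"; nothing else is lost.

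Withdrawal has its own provisions. Section 12.0 says: "If a participant withdraws from the study, they will only receive compensation for the surveys they complete". Section 15.0 covers voluntary withdrawal and removal by the study lead, for example after a stroke.

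The Aim 1 analysis (section 8.0, Statistical Analyses) is a generalized linear mixed model over months 0 to 36 that does not need complete records. The exit rule appears only in section 12.0. Neither the eligibility criteria (section 3.0) nor section 8.0 mentions it.

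**The concern.** The rule joins two different events with and/or. Someone who never finishes the website session has not had the planned exposure, and a study of what follows PYL could reasonably leave that person out. Someone who finishes the session and misses only the post-test has had the exposure, so the same reasoning does not explain the exit.

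For that second person the plan gives up every later outcome, including the primary one, because of one missed 15-minute questionnaire. A participant who misses a 15-minute phone survey is simply called again at the next wave. The mixed model can accommodate a missing post-test, but it has no post-visit outcomes for someone who is never called.

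The decision is also one-way. If everyone exposed is followed, an analysis restricted to post-test completers can still be run. If they are not followed, the wider analysis cannot be recovered later. Replacement is difficult too: the target is 700 (section 4.0), and the only source is a cohort of about that size (sections 3.0 and 10.0).

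**Working it through.** **1. The plan's own figures (sections 8.0 and 12.0).**
- Visit: 10 + 30 + 15 + 15 = 70 minutes, up to 10 + 30 + 45 + 15 = 100 minutes.
- Phone surveys: 8 × 15 = 120 minutes. Total: 190 to 220 minutes.
- Payment: 25 + 50 + 25 = $100, plus 8 × 50 = $400, giving $500.

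All of these agree with the text. The sample size of 700 cannot be reproduced, because section 4.0 mentions power calculations without giving their inputs. The effect on planned power therefore cannot be stated.

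**2. The participant who misses only the post-test.**
- Time already given: 10 + 30 + 15 = 55 minutes to 10 + 30 + 45 = 85 minutes.
- Post-test as a share of planned time: 15/220 to 15/190 = 6.8% to 7.9%.
- Forfeited phone surveys as a share: 120/220 to 120/190 = 54.5% to 63.2%.

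These shares show how uneven the rule is. They measure neither bias nor precision.

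**3. Cost of keeping that person.** Gift cards: 8 × $50 = $400. Total payment: 25 + 50 + 400 = $475, below $500. Expected survey time: 8 × 15 = 120 minutes. Section 8.0 allows up to five calls per wave, so up to 8 × 5 = 40 call attempts, plus voice mails. The 120 minutes is therefore not a ceiling on staff time.

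**4. Illustration of size.** The documents give no exit rate. Let e be an assumed exit rate among 700 baseline completers, with other dropout ignored. Those who miss only the post-test are a subset of all visit-day exits, so a row chosen for all exits is an upper limit for this group.
- Standard error increase: 1/√(1 − e) − 1.
- Shift in the share with a decision at month 36 (followed minus all): p_f − [(1 − e)p_f + e·p_x] = e × (p_f − p_x), where p_f and p_x are the shares among those followed and those who exit. Differences of 10 and 30 points are assumed.

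| e (assumed) | People | Surveys not sought | SE increase | Shift, 10-point difference | Shift, 30-point difference | Gift cards, at most | Expected survey hours |
|---|---|---|---|---|---|---|---|
| 1% | 7 | 56 | 0.5% | 0.1 | 0.3 | $2,800 | 14 |
| 2% | 14 | 112 | 1.0% | 0.2 | 0.6 | $5,600 | 28 |
| 5% | 35 | 280 | 2.6% | 0.5 | 1.5 | $14,000 | 70 |
| 10% | 70 | 560 | 5.4% | 1.0 | 3.0 | $28,000 | 140 |
| 20% | 140 | 1,120 | 11.8% | 2.0 | 6.0 | $56,000 | 280 |

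For comparison, the 95% confidence half-width for a share of 50% is 1.96 × √(0.25/700) = 3.7 points, and 4.1 points with n = 560. Nine of the ten shifts are below 3.7 points. Only 20% exit combined with a 30-point difference exceeds the half-width.

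**The case against.** The benefit may be very small. The visit is supervised and staff help with navigation. The post-test is short, and finishing it earns $25. Some people who leave at that point may in effect be withdrawing, and those who stay in follow-up may respond less often than others, so the standard error gains above are upper limits. The figure of 700 is also a ceiling, because the source cohort is about that size before the device criterion, the prior-participation exclusion and refusals. All of this stands, and it limits the weight of the point.

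Missing outcomes are also partly handled. Nothing says that visit-day data or linked LitCog data of people who exit are discarded. If exit depends only on variables in the model, a likelihood-based analysis has about zero bias. A reader might infer that the rule biases the month-36 result; the documents do not show this, and neither size nor direction is known.

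A reader might also infer that everyone who completes the baseline survey must be followed, or that the rule breaches intention-to-treat. The documents do not support either. There is one group and no randomisation. Aim 1, "Determine how decision making and planning for aging-in-place is impacted by" age-related changes and social influences, is not limited to website completers. But section 2.0 presents the unanswered question as what happens after PYL beyond three months, and section 8.0 makes the website part of the first visit and its usage a mediator. Following only exposed people is defensible. Paying up to 25 + 400 = $425 to someone who does not finish the session could also weaken the incentive to finish it.

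None of this explains dropping a person who finished the session.

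**Conclusion.** The point holds in a narrow form and is worth considering. For participants who completed the baseline survey and the website session and missed only the post-test, the exit rule has no stated reason. An exposed-cohort rationale does not cover them, the Aim 1 model does not need the rule, and it sits badly beside the continued outreach after a missed phone survey.

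The size is modest. Each person retained adds up to eight surveys, one of them at the primary time point. The number of such people is not documented and is probably small. The exit rates, group differences and 50% share used above are assumptions, and across most of that range the effect is below sampling error. The case rests on low cost and on the fact that outcomes never sought cannot be recovered, not on demonstrated bias or a material loss of power.

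Whether to follow people who did not finish the website session is a genuine design choice, and the documents do not settle it.

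**What to change.** 1. Amend section 12.0 so that anyone who completed the baseline survey and the website session, and has not withdrawn, stays eligible for all eight phone surveys whether or not the post-test was done.
2. State this rule in section 8.0, where the procedures and analysis are described.
3. Report the number and baseline profile of people who exit at the visit.
4. Optional: also follow baseline completers who did not finish the website session, flagged by exposure, and report both exposed-only and all-participant analyses. Otherwise, state in section 8.0 that the followed population is website completers.

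Items 1 to 3 need protocol and consent wording, plus the per-person cost in step 3 of the working. They add no unexposed people to the analysis. Item 4 has the same gift-card ceiling per person, but brings in people with little or no PYL exposure and may weaken the incentive to finish the session.
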